#### Screening protocol

Briefly, we will first screen men with total PSA and then use an array of four biochemical markers (4Kscore) among men with PSA>3 ng/ml to improve the diagnostic accuracy for clinically significant cancer (Gleason≥7), while reducing the number of biopsies and detection of Gleason<7 cancers. For diagnostic assessment of screen-positive men, we will use multiparametric MRI, aimed at reducing the detection of Gleason<7 prostate cancer by at least 50% by the combination of the screening test and diagnostics (Figure 1). Finally, the baseline serum PSA is used for determining the optimal screening interval, ranging 2-6 years.

[figure not shown]

Figure 1. Using three layers of risk stratification to identify men at highest risk.

The control arm will receive usual care, with no intervention (apart from collection of registry data for all men in both arms on the outcomes, including PSA testing, prostate cancer incidence and mortality, as well as questionnaire surveys for some subgroups).

Men in the screening arm will be invited to the first screen over a two-year period. We expect similar participation as in the previous Finnish prostate cancer screening trial (two thirds or 11,167 participants). This would mean that we would screen roughly 560 men per month (assuming 10 months of effective screening annually) (Figure 2).

In the baseline survey at entry to the study, screening participants are asked about their family history of prostate cancer, as well as established or suspected risk factors for prostate cancer (including BMI, alcohol consumption, physical activity and consumption of some foodstuffs). Information will be also collected on previous PSA tests and possible prior prostate biopsy from the hospital databases.

A 30 ml blood sample will be drawn at one of the service sites of the regional laboratory networks (HUSLab and FimLab) to an EDTA tube, with plasma and serum separated and frozen. Total and free PSA are analysed at HUSLab and FimLab with electrochemiluminescence immunoassay (ECLIA) for COBAS® 6000 analyser (Roche Diagnostics, Rotkreuz, Switzerland). Calibration is performed using the WHO standards (WHO 96/670 and 68/668 for total and free PSA).

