Based on the FinRSPC first round results, we expect that the proportion of men with  $PSA \geq 3$  is 13% overall (10% in men aged 53-57, 17% for ages 58-62 and 24% at ages 63-65), total expected  $N=1452$ . This would mean on average 75 kallikrein panel determinations per month.

Screening interval is based on the initial PSA: men with  $PSA \geq 3$  are re-invited after two years, those with  $PSA > 1.5$  after four years, and the men in the lowest risk group ( $PSA < 1.5$ ) after six years.

After serum PSA as the initial test, we will use a four-kallikrein panel (4Kscore) to identify men at an increased risk of a clinically relevant prostate cancer. The determinations will be performed by prof. [name] in his lab in Malmö, with samples shipped every two weeks. These men will be referred to MRI and only MRI-positive men will be biopsied (randomised to targeted biopsy alone versus targeted and systematic biopsy).

The men with the highest risk of Gleason 7+ prostate cancer based on the kallikrein panel (out of those with  $PSA > 3$ ) will be regarded as screen-positive and referred to diagnostic examination at Tampere or Helsinki University Hospital urology clinic. The expected frequency is 871 men in the first round (60% of men with  $PSA \geq 3$ , or 7.8% of all participants), on average 45 men referred to MRI each month. This is substantially lower than in the PSA-based ERSPC trial (where on average 13% of the participants were screening-positive and referred to biopsy in the first round).

[figure not shown]

Figure 2. A CONSORT diagram illustrating the trial protocol and the expected distribution of men by test results

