#### Diagnostic procedures

The screen-positive men will undergo a multiparametric MRI using 3T equipment (Siemens Achieva) with 32-channel pelvic phased-array coil. T2-weighted, diffusion-weighted and dynamic contrast-enhanced imaging is employed in accordance with the European Society for Urogenital Radiology guideline. The findings will be classified according to the Prostate Imaging Reporting and Data System (PIRADS-2), which is a 5-point scale to combine the MRI findings and indicate the likelihood of a significant cancer (Osses 2017). A score of 4-5 indicates a PPV > 80% and also a score of 3 is regarded as a positive finding warranting biopsy. Standardisation of MRI procedures is ensured prior to the start of the trial, including slice orientation and thickness, and size of the matrix and field of view. Training sessions will be repeated annually throughout the conduct of the trial. Independent double reading for a random sample of the images is used for quality assurance, and to reduce false negative and false positive findings. Standardised and structured radiologists' reports will be obtained and prostate volume also recorded. Pseudoanonymised images are uploaded into the cloud-based trial database using the ECRF software tailored for the trial purposes.

The men with positive MRI will undergo targeted biopsy using fusion MRI-TRUS guidance (UroNav), with an additional core per each incremental 6 mm size of the lesion. The expected frequency of positive MRI is 60% of screen-positive men (4.7% of all screening participants), with a total of 521 men in the first round. To avoid missing cancers among high-risk men, those with PSA density (serum PSA divided by prostate volume) > 0.15  $\mu\text{g}/\text{ml}^2$  will be referred to systematic biopsy despite a negative MRI (Distler 2017). A random sample of those men with PSA  $\geq 3$  but (1) negative kallikrein panel and/or (2) negative MRI will also undergo systematic biopsy for assessment of diagnostic accuracy. A small number of men will not be eligible for MRI due to metal implants, and for them transrectal ultrasound (TRUS) will be used instead.

The prostate biopsies are evaluated by trained, experienced uropathologists under supervision of [name] in Helsinki and [name] in Tampere. Structured and standardised reports are used, with each core is evaluated separately and exact location recorded. Training and standardisation will be conducted

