#### Data collection

Cost data will also be collected for economic analyses, including procedure codes, DRG group and actual billing information for each hospital visit (including outpatient visits) from the hospital database.

Questionnaire surveys will be used for random samples of men in both arms to obtain utility estimates (with the 15D instrument) and information on out of pocket health care costs. For indirect costs, data on sickness benefits will be obtained from the Social Insurance Institution (SII) database (the governmental agency providing all benefits through the national comprehensive health insurance system).

Adverse effects of biopsy are evaluated, with questionnaire surveys of complications, including assessment of bleeding, lower urinary tract symptoms (LUTS) and erectile dysfunction (ED) at four weeks (with baseline data on LUTS and ED prior to biopsy collected at the time of the examination), as well as hospitalisation data on septic infections. The questionnaire instruments used are ICIQ-MLUTS for LUTS and IIEF-5 for ED; in addition, data on antibiotic prescriptions following biopsy will be obtained from the SII nationwide prescription database.

Information on prostate cancer cases diagnosed in the entire study population will be obtained from the Finnish Cancer Registry (with >99% coverage of cancer cases in Finland), so that interval cancers as well those in non-participants and the control arm can be identified and intention to screen analyses of prostate cancer incidence in the entire study population conducted. Detailed clinical information on Gleason score, PSA at diagnosis, treatment and other features will be retrieved from the electronic medical record using the ECRF software customised for the trial.

As for patient-oriented outcomes, assessment of the generic quality of life (SF12 and 15D) will be conducted for a sample of men at each stage of the screening process. The validated Extended Prostate Cancer Index Composite (EPIC) questionnaire is used for monitoring quality of life and adverse effects of treatment in all men within trial diagnosed with prostate cancer (regardless of arm, hospital and treatment).

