## 5. TRIAL SCHEDULE

The study will commence in 2018, with randomisation of half of the men during the first year. The first screening round will be completed in 2019. A summary of the timeline is shown in Table 1.

Table 1. Planned schedule of the trial conduct

	Trial years 1-2	Years 3-4	Years 5-6	Years 7-8	Years 9-10
All subjects	Recruitment				
All participants	1 st screening				
Men with PSA>3		2 nd screen	3 rd screen	4 th screen	5 th screen
Men with PSA 1.5-3			2 nd screen		3 rd screen
Men with PSA<1.5				2 nd screen	

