## 6. POWER CALCULATIONS & STATISTICAL ANALYSIS PLAN

The main outcome of the trial is prostate cancer mortality. An intention to screen analysis will be performed, with all men in the groups defined by random allocation, regardless of compliance. This is the gold standard for randomised trials, as it gives an unbiased effectiveness estimate, which is realistic for application (though lower and 'diluted' compared with an efficacy estimate based on compliers only). The only post-randomisation exclusions will be based on prostate cancer diagnosis prior to entry, as inevitably some recent cases will be found out only after randomisation. Follow-up starts at randomisation, and ends at death. Dates of death are registered also for men who have emigrated, but in case of a missing cause of death, the event will be censored. Cox regression will be used with prostate cancer death as the outcome. Randomisation is expected to result in balanced distribution of age, with no need for adjustment.

Based on the most recent age-specific population rates (2010-2014) and the age structure of the male population, the expected number of prostate cancer deaths in the control arm is 222 at 10 years, with sufficient statistical power ( $1-\beta=0.8$ ,  $\alpha=0.05$  two-sided) to detect a 33% reduction (hazard ratio,  $HR\leq 0.67$  for the screening arm, cumulative mortality 29 vs. 44 per 10,000 men) in prostate cancer mortality. This is calculated considering the overall mortality from other causes (ranging from 7 per 100,000 at age 55 to 210 per 100,000 at age 75), yielding a total of 475,000 person-years of follow-up. At 15 years of follow-up, the expected number of deaths in the control arm is 451, with a minimal detectable effect size of 26% ( $HR\leq 0.74$ , 67 vs. 90 deaths per 10,000 men, based 912,800 person-years of follow-up).

A secondary analysis of prostate cancer mortality will be performed using the Cuzick method to correct for non-compliance and contamination (Cuzick 1997, Roobol 2009, Kilpeläinen 2015).

Intermediate outcomes include cumulative incidence of advanced (T3-T4 or M1) prostate cancer (number of cases relative to population size, not using incidence density to avoid the lead-time bias due to early

detection by screening), and cumulative incidence of low-risk cancer (Gleason<7) as an indicator of overdiagnosis.

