Analysis of screening test performance, including sensitivity and specificity, positive and negative predictive value will be conducted, assessing also the accuracy of 4Kscore and MRI. Interval cancer incidence will be analysed as an indicator of program sensitivity, besides participation and its determinants. Cancer detection and screening test performance will also be evaluated by major risk factors including family history, genetic risk and major lifestyle determinants.

Short-term quality of life impact of screening will be evaluated among screening participants, and adverse effects of prostate biopsy analysed as outlined above. Quality of life and psychosocial impacts among men diagnosed with prostate will be assessed using the EPIC instrument and the Memorial Anxiety Scale for Prostate Cancer (MAX-PC), enrolling screen-detected and interval cases, as well as those diagnosed among non-participants and in the control arm. Follow-up will be carried out at diagnosis and 6, 12 and 48 months after it. A mobile phone app is used to collect data on patient-oriented outcomes.

Economic evaluation will commence with cost analysis, and the final analysis of incremental cost effectiveness ratio (with a decision analysis) can be conducted only once data on both long-term cost and real outcome data on both utilities (quality-adjusted life-years) and mortality are available. However, early assessment can give some predictions about potential effects size required for the intervention to be regarded as cost-effective.

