## 7. ETHICAL ISSUES

Screening is by definition targeting people free of the target condition, and the benefit per participant is nearly always small. Consequently, any risk must also be small to justify the intervention. The primary screening tests are based on biochemical analyses of a blood sample, with minimal risks. All the other procedures in the trial (diagnosis and treatment among screen-positive men) are conducted in accordance with the normal standards of care and pose therefore no ethical issues. The study protocol will be submitted for review by the ethical committees of the Uusimaa and Pirkanmaa hospital districts. Permission for cancer registry linkage will be obtained from the National Institute for Health and Welfare (THL). Written informed consent is obtained from all screening participants for both the intervention and collection of data from electronic health records and health care registers for the analyses of the trial (cancer registry, cause of death registry, hospital discharge registry, regional laboratory and national prescription databases). Information about screening covers probabilities of abnormal screening test result, prostate cancer detection at biopsy given screen-positive result, frequency of biopsy complications, treatment options with their adverse effects, overdiagnosis in screening, as well as mortality impact of screening. The information is provided as a decision aid with graphically presented numerical results, modified from the earlier Finnish screening trial. A trial website will also be constructed to provide information on the progress of the study for the participants. According to the Finnish regulation, no consent is required for non-compliers or men in the control arm, but register data can be collected with permission from THL after an ethics committee review.

The trial can be stopped early for benefit or harm, if evidence for difference between the arms is obtained. For assessment of harm from the intervention, biopsy and treatment complications will be analysed, as well as incidence of advanced cancer (as an indicator of cancers missed by screening) and Gleason <7 cancer (as indicator of overdiagnosis) by arm are performed annually for the data monitoring committee. Monitoring of the main end-point (prostate cancer mortality) is carried out by an external committee. Interim analyses

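### The by-arm Gleason<7 overdiagnosis indicator counts cancers found only by accuracy-verification biopsies in the screening arm, and no algorithm-only cumulative incidence is planned beside it

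*Combined protocol and SAP*

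**What the plan says.** All references are to the combined protocol and SAP.

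- Section 6 lists among the intermediate outcomes the "cumulative incidence of low-risk cancer (Gleason<7) as an indicator of overdiagnosis", calculated as cases over population size. The only post-randomisation exclusion there is a prostate cancer diagnosis made before entry.
- Section 4, Data collection, takes cases from the cancer registry so that interval cancers, non-participants and controls are all covered and "intention to screen analyses of prostate cancer incidence in the entire study population conducted".
- Section 7 provides that analyses of "Gleason <7 cancer (as indicator of overdiagnosis) by arm are performed annually for the data monitoring committee".
- Section 4, Diagnostic procedures, says that a random sample of men with PSA of at least 3 and a negative kallikrein panel and/or "negative MRI will also undergo systematic biopsy for assessment of diagnostic accuracy". The sampling fraction is not stated, nor is whether sampling happens once or at every screen.
- Section 4, Screening protocol, gives the control arm usual care without intervention, apart from registry data and some surveys.
- Section 6 also plans sensitivity, specificity and predictive values, "assessing also the accuracy of 4Kscore and MRI". It gives no rule for handling verification-biopsy cancers in the incidence comparison between arms.

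**The concern.** The verification biopsies answer a research question about the tests. A screening programme would not do them, and controls do not have them. Systematic biopsy of test-negative men can find low-grade disease, which is what the algorithm is meant to leave undetected. No sentence says that these cancers count towards the overdiagnosis indicator. It follows from an outcome without a detection-route restriction, complete registry ascertainment and a single exclusion rule.

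Two quantities are thus merged. One is the low-grade cancer that men allocated to screening actually experience in this trial. The other is the low-grade cancer that the three-step algorithm would generate if adopted. The Study rationale needs the second, because half of its hypothesis is that the algorithm largely removes overdiagnosis, and it ties the introduction of screening to the answer. Only the first is planned as a by-arm figure. The data monitoring committee receives that figure each year and, as planned, could not see how much of any excess comes from research biopsies.

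**Working it through.** **1. The plan's own counts.** Two thirds of 16,750 men gives 11,167 participants. Then 11,167 × 0.13 = 1,452 with PSA of at least 3; × 0.60 = 871 panel-positive; × 0.60 = 523 MRI-positive (stated: 521). Expected screen-detected cases are 0.026 × 11,167 = 290, as stated. With 75-80% at Gleason 7 or above, 20-25% of 290 gives 58 to 73 Gleason<7 cases from the algorithm in round 1.

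**2. Men open to verification in round 1.** Panel-negative: 1,452 − 871 = 581. MRI-negative: 871 − 521 = 350. Total 931. This is an upper bound for the round, because MRI-negative men with PSA density above 0.15 have systematic biopsy under the algorithm itself and leave the pool.

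**3. Net excess, one sampling occasion.** Let f be the fraction sampled, y the Gleason<7 yield and q the probability that a man in the pool would later be counted as a Gleason<7 case anyway. Then

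extra = pool × f × (y − q).

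The documents give none of f, y or q. They also give no expected number B of Gleason<7 cases in the whole screening arm, which includes 16,750 − 11,167 = 5,583 non-participants, interval cancers and all later screens. B = 200-300 is an assumption. The control count does not change, so the ratio between arms is multiplied by 1 + extra/B.

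| Assumptions (one occasion) | Extra cases | B = 300 | B = 200 |
|---|---|---|---|
| 931, f 10%, y 15%, q 5% | 9.3 | +3.1% | +4.7% |
| 931, f 20%, y 15%, q 5% | 18.6 | +6.2% | +9.3% |
| 931, f 10%, y 15%, q 10% | 4.7 | +1.6% | +2.3% |
| 581, f 5%, y 10%, q 5% | 1.5 | +0.5% | +0.7% |
| 931, f 20%, y 20%, q 5% | 27.9 | +9.3% | +14.0% |

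The first two rows, in absolute terms, are 9.3/16,750 = 5.6 and 18.6/16,750 = 11.1 per 10,000 men. If y = q, the excess is zero. The formula treats every selected man as biopsied, so refusals lower it.

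**4. If sampling recurs.** The Table 1 row "Men with PSA>3" in Section 5 shows up to five screens. The text neither states nor excludes verification at each. With y = 15% and q = 5%, extra = 931 × 0.10 × [1 − (1 − f)^5]. At f = 10% this is 93.1 × 0.410 = 38.1 cases; at f = 20% it is 93.1 × 0.672 = 62.6. On B = 200-300 these are +13% to +19% and +21% to +31%.

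**5. Which correction works.** Deleting verification cancers over-corrects, because some would have surfaced later. At f = 20%, one occasion, it loses 931 × 0.05 × 0.20 = 9.3 genuine algorithm cases, so a true 200 becomes about 191. Selection is random, so men can instead be censored at selection and unselected men in the same stratum weighted by the inverse of their cumulative probability of non-selection. In a simulation with B = 200 or 300, f = 10% or 20%, and one or five occasions (15% latent, one third surfacing evenly over rounds 2-5), the mean weighted count matched the true count to within 0.1 case. With five occasions at f = 20% and a true 200, a single 1/(1 − f) weight gave 188, so the weight must be the product over occasions.

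**6. Precision.** Of B, 931 × 0.05 = 46.6 cases arise in the pool. Treating counts as Poisson, the standard error ratio is approximately √[(B + 46.6 × (w − 1))/B], with w the mean weight of pool cases. One occasion: w = 1.11 (f = 10%) or 1.25 (f = 20%), so the standard error rises by 1% to 3%. Five occasions: w is the mean of 1/(1 − f)^k for k = 1 to 4, which is 1.31 or 1.80, and the rise is 2% to 9%. The largest weight after five occasions is 1/0.9^5 = 1.69 or 1/0.8^5 = 3.05.

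**The case against.** The strongest reply is that the planned outcome is the right one. Participants do bear the consequences of a verification-found cancer, so an all-cancer intention-to-screen count is the proper measure of harm in the trial. The distortion runs against the trial's hypothesis and cannot produce a false claim of reduced overdiagnosis. No test, alpha or threshold is attached to Gleason<7. All of this stands. It is why the main analysis should not change and why this is an improvement rather than a flaw in the primary result. It does not supply the figure that the hypothesis about the algorithm needs.

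A second reply is that Section 6 already plans accuracy analyses, which require sampled test-negative men to be identifiable, and that Section 4 counts screen-detected cases by Gleason group. This narrows the point. Algorithm-only detection among participants could be derived; what is absent is an algorithm-only cumulative incidence by arm.

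A third reply is that weighting is elaborate for what may be a few cases, and that a table by detection route would do. Such a table is useful, but subtracting its verification row gives the over-correction shown in step 5.

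**Conclusion.** The point holds as one about definition and planned analysis. As written, the by-arm Gleason<7 indicator includes research-biopsy cancers in the screening arm only, and no by-arm algorithm-only figure is planned. The direction is known; the size is not. About +3% to +9% rests on an assumed 200-300 arm cases, one occasion, f = 10-20%, y = 15% and q = 5%. Other plausible inputs take it close to zero, and sampling at every screen would make it larger. The primary mortality analysis and its power calculation do not use the indicator.

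Three stronger inferences are not supported:

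- A reader might divide the extra cases by the 58-73 first-round cases, or a slightly larger pool-based count, and report much larger percentages. The indicator covers all 16,750 men over all rounds, so that base is wrong.
- A reader might say that the target "aimed at reducing the detection of Gleason<7 prostate cancer by at least 50" per cent would be read as missed. The Screening protocol sets that target for detection by the screening test and diagnostics combined, without a stated comparator. It is not a contrast in cumulative incidence with usual care.
- A reader might add the randomisation of MRI-positive men between two biopsy strategies as a further bias. The pooled figure is unbiased for the mixture delivered, so this is a separate matter of reporting.

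The PSA-density biopsies belong to the algorithm and are not at issue.

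**What to change.** In Section 6:

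- Keep the all-cancer intention-to-screen Gleason<7 comparison as the main analysis and for harm monitoring.
- State the verification sampling fraction by stratum (panel-negative, MRI-negative) and by screening round, and record the biopsy route of every cancer.
- Pre-specify one secondary algorithm-only Gleason<7 cumulative incidence. Censor a man when he is selected for verification, whether or not he accepts, because selection is random and acceptance is not. Weight unselected men in his stratum by the inverse of their cumulative probability of non-selection: 1/(1 − f) for one occasion, the product over occasions otherwise. Divide the weighted case count by all men randomised to the arm.
- Give the data monitoring committee both versions.

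The cost is one data field, documented sampling fractions and one extra analysis. Sampled men must be identifiable for the accuracy analysis anyway. The secondary estimate loses some precision (about 1-3% in standard error if sampled once, 2-9% over five screens, under the assumptions above). No clinical procedure changes.
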